Easy Stretch Toolkit: A Pilot Study

Co-Investigators: [name] and [name]

Funding Sponsor: UTMB Health Technology Commercialization Program

Version 10/October 2020

Efficacy of the Easy Stretch Toolkit: A Pilot Study

1. Introduction and Purpose:

The Easy Stretch Toolkit (patent pending) is a set of three novel intraoral tools designed to deliver a passive stretch to scarred or contracted orofacial musculature, with the goals of: 1) increasing measurable range of motion for multiple facial muscles and tissues, and 2) reducing the impact and appearance of scar tissue. We designed the Easy Stretch Toolkit for patients negatively impacted by facial burns. We propose a pilot study to test if the tools can directly target multiple sites across the face, with particular attention to the cheeks, nasolabial folds, upper lip, mentolabial junction and modiolus, achieving a stretch that currently available tools cannot provide. We hypothesize that there will be an expected gain of improved ability to increase use of orofacial musculature, as well as improved range of facial expressions and related motor functions in patients with facial burn injury. The Easy Stretch Toolkit is proposed for use with adults and children over the age of 7 in this pilot study. Use of the device(s) is intended to be utilized by a trained Speech Pathologist. The exact tool to be used will be selected by the Speech Pathologist based on the patient's specific deficit areas and needs. In this pilot study, investigation into the efficacy of the Toolkit will be limited to subjects with chronic facial burns, with future plans to expand the project to subjects of all ages in the acute healing phase if preliminary results prove the tools are effective. Physical prototypes were created with the assistance of the MakerHealth Space Lab at UTMB, following the designs and initial prototypes of the creators (patent pending). See Appendix A. The current treatment options for patients with scars secondary to orofacial burns are discussed in the Background and pictures of tools are shown in Appendix B-F. Because our tools are similar, and in some ways potentially safer than the current tools available in the market, we believe that the Easy Stretch Tools are a minimal risk device. This product represents an advance in the care of these patients. There is minimal risk associated with correct use of the product (discomfort from stretching, bleeding if facial burn sites are not fully healed, possible allergy from intraoral contact with food-grade silicone, remote choking risk, asymmetrical range of motion, remote tearing of the mucous membrane); the expected benefits are that the tools will increase mobility of the orofacial skin and musculature, as well as reduce and possibly prevent burn-induced scar formation. This protocol and enrollment procedures are revised due to the Covid -19 Pandemic to allow for increased ability to enroll participants due to the University's restrictions on travel.

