All tools are hand washable and will belong to the patient (will not be used between patients). Tools include the circle tool (yellow), bar tool (blue), L tool (green). See Appendix G for proposed placements.

This study will be conducted as a single-subject design. Each patient will serve as his/her own control based on the purpose of the study and the large heterogeneity among patients. Conditions which would result in participant exiting the study might include: non-compliance, subject withdrawal of consent, unexpected need for additional surgeries during the treatment period.

Proposed data points (see below) were adapted from the study completed by Hadlock and Urban [7]. In their 2012 study, they assessed resting facial distance relationships and changes in these relationships during movements to form different facial expressions using a novel device called Facial Assessment by Computer Evaluation (FACE). The creators of the Easy Stretch Toolkit will use UTMB customized facial measurement software designed for this study to measure pre- and post-use change. See Appendix K. The specific measurements to be taken during selected facial movements are discussed below.

4. Study Procedures:

Protocol

In this initial pilot study, we will recruit 20 adult or pediatric patients who have sustained facial burns or who have sustained a facial injury. A facial injury can be any disorder that results in scarring, tightness, limited range of motion of facial skin or musculature or fibrosis. For the purpose of this study, facial burn injury or facial injury will be defined as an injury to the midface or lower half of the face and may be unilateral or bilateral. Participants must be in the chronic phase of recovery to complete the 8 week treatment. Chronic burns are defined as those burns that are not in the acute

[name] and [name]

Version 10/October 2020

Page 5 of 24

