The primary outcome will be change in degree of facial movement during different facial expressions as described above pre- and post-study. The secondary outcome will be any improvements in quality of life pre- and post-study as captured by the Facial Disability Index. The Facial Disability Index will be used as a validated quality of life instrument [12]. See Appendix M. Although it is somewhat dated (1996) and it was intended for use with facial neuromuscular disorders and facial palsy, its questions were deemed the most relevant for this study after thorough review of available burn, facial palsy and general quality of life measures.

The subjects will not be responsible for any research-related costs; insurance companies will not be billed. Validated parking will be offered if attending visits in person.

5. Sub-Study Procedures:

Not applicable.

6. Criteria for Inclusion of Subjects:

We plan to recruit 20 adult or pediatric patients who have sustained facial burns or who have sustained a facial injury resulting in scarring, tightness, limited range of motion of facial skin or musculature or fibrosis and are in the chronic phase of recovery to complete the 8 week treatment.

1. Age 7-80
2. Male or Female Sex
3. Patients who have sustained a facial burn and are now in the chronic phase, or any patient experiencing facial tightness or limited range of motion due to other problems, including patients s/p radiation to the head and neck, trauma, scarring and scleroderma
4. Chief complaint(s) of limited mouth opening, difficulty chewing or speaking, decreased range of motion for oral structures, and/or limited facial expressions
5. Subject or caregiver (parent or guardian, in case of pediatric population) must be able to give informed consent
6. Subject or caregiver (parent or guardian, in case of pediatric population) must be able to perform exercises at home and must be able to record time spent using the devices.
7. Participants who are undergoing other treatment methods such as use of compression garments, skin grafting, radiation or other facial surgery, etc must suspend all of these treatments for the duration of the 2 month trial.
8. Internet access including access to FaceTime, Skype or Zoom and email access if electing telehealth option for enrollment

7. Criteria for Exclusion of Subjects:

The following will exclude patients from participation in the study:

[name] and [name]

Version 10/October 2020

Page 9 of 24

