1. planned or unplanned surgeries for facial skin grafting around lips or nose or oral commissure release during the upcoming 8 weeks
2. completion of any massaging or other stretching exercises or programs not specified by the creators
3. use of new creams or topical treatments for the duration of enrollment in the study.
4. acutely burn-injured patients
5. incarceration, or pregnancy

9. Sources of Research Material:

We are collecting clinical and demographic data from the electronic charts. We are also collecting data as shown in Appendix H, I, J, K, L. These will be obtained via photographs of the subject during different facial expressions which are uploaded into a software program for measurements to be taken.

9. Recruitment Methods and Consenting Process:

The investigators will request a HIPPA Waiver to identify potential subjects. Potential subjects may be patients or former patients of the investigators. Additionally, they may be identified via clinic lists or outside referral sources. The potential subjects will be identified / referred by any clinician or physician and their patient(s) will be sent a recruitment letter or informational pamphlet with the approval of the referring clinician/physician (see Appendix L, as well as recruitment brochure).

To further clarify, the investigators will pursue various methods for recruiting subjects, including UTMB or outside physician referrals, outside speech pathologist referrals, referrals from other professionals and community engagement activities. We do not plan a multisite study, but seek the option to widen the scope of patient referrals by contacting other burn centers and burn support groups and through participation in community outreach activities. The physicians will be asked to refer eligible patients; the physicians would not be engaged in the research. Subjects will be seen at their place of residence or UTMB outpatient clinics or via telehealth. Subjects may self-refer from marketing materials. Outreach will include social media, such as postings to burn support group websites or Facebook pages, Speech Pathology special interest group pages, Facebook, UTMB Department of Otolaryngology Facebook page. In all recruitment scenarios, the investigators will notify the subject's managing physician of their participation in the study. If the subject cannot be reached by phone, a letter will mailed to the potential subject with study information.

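### Section 1 limits the trial to chronic facial burns, but Sections 4 and 6 enrol facial injury of any cause and Section 14 analyses all causes together without a breakdown

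*Combined protocol and SAP*

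**What the plan says.** **Population.** Section 1 (Introduction and Purpose) says that "investigation into the efficacy of the Toolkit will be limited to subjects with chronic facial burns". Its hypothesis concerns "improved range of facial expressions and related motor functions in patients with facial burn injury". Section 4 (Study Procedures) recruits 20 patients "who have sustained facial burns or who have sustained a facial injury", and defines the second group broadly: "A facial injury can be any disorder that results in scarring, tightness, limited range of motion of facial skin or musculature or fibrosis". Inclusion criterion 3 in Section 6 admits burns and also "any patient experiencing facial tightness or limited range of motion due to other problems". Its examples are scleroderma, trauma, scarring and earlier head-and-neck radiation.

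**Chronic phase.** Section 4 says of everyone: "Participants must be in the chronic phase of recovery to complete the 8 week treatment". The opening sentence of Section 6 applies the same condition to burns and other facial injury. Inclusion 3 attaches it only to burns: "Patients who have sustained a facial burn and are now in the chronic phase, or any patient experiencing facial tightness". Exclusion 4 in Section 7 removes only "acutely burn-injured patients". The definition of chronic in Section 4 is written for burns.

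**Analysis.** Section 14 (Biostatistics) takes as primary outcome the post-minus-pre change in millimetres for each facial expression, tested with paired t-tests or a non-parametric alternative. It names no table, estimate or test by cause of injury. Its sample size is 20, allowing for 10% missing, for an effect size of 0.7 with power 0.8 at two-sided 0.05.

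**The concern.** The introduction and the eligibility criteria of the same protocol version describe different trials. A reader of Section 1 would take a significant change as evidence in chronic burns. A reader of Section 6 would know only that some mixture of causes improved. Nothing in the plan sets the burn share or commits to reporting it.

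This matters for two later decisions. Section 1 makes the results the basis for moving to patients in the acute healing phase. The end of Section 2 says a larger trial will be powered from the effect sizes seen here. An effect size of unknown burn content is a weak basis for either.

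The uneven wording on the chronic phase adds a smaller problem. The recruitment section says that subjects are screened with an eligibility checklist and the inclusion and exclusion criteria. A screener working from the numbered items finds no chronic-phase rule for a non-burn patient. The general statement elsewhere does not say what a chronic phase of recovery means for, say, scleroderma. Using each patient as his or her own control removes fixed differences between patients. It does not remove change over the 8 weeks from healing or disease course, so the state in which non-burn patients enter affects how a pre-post change is read.

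**Working it through.** **1. The passages side by side**

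| Place | Causes covered | Chronic-phase condition |
|---|---|---|
| Section 1, scope and hypothesis | Burns only | Yes, for burns (scope sentence) |
| Section 4, recruitment | Burns or any facial injury | All participants; defined for burns only |
| Section 6, opening | Burns or any facial injury | All participants |
| Section 6, inclusion 3 | Burns or any other cause | Burn limb only |
| Section 7, exclusion 4 | Burns only | Acute burns only |
| Section 14 | All enrolled, no split | Not mentioned |

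Row 1 cannot be true together with rows 2 to 4. Rows 2 and 3 supply a chronic-phase condition for everyone. Rows 4 and 5 fail to carry it through.

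**2. The plan's own figure**

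Inputs from Section 14: N = 20, 10% missing, d = 0.7, two-sided alpha 0.05, paired t-test.

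- Evaluable: 20 × (1 − 0.10) = 18.
- Power = P(|T| > t(0.975, n − 1)), where T is noncentral t with n − 1 degrees of freedom and noncentrality d√n.
- For n = 18: noncentrality 0.7 × √18 = 2.970, critical value 2.110, power 0.799.

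The stated 0.8 reproduces. It refers to all evaluable patients, whatever the cause.

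**3. What the same design gives for burns alone**

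The documents give no burn share, so the number of burn patients among the 18 is an assumption, shown as a range. The last column is the half-width of a 95% confidence interval for the mean change in SD units, t(0.975, n − 1)/√n.

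| Evaluable burn patients | Noncentrality 0.7√n | Critical t | Power at 0.7 | Effect detectable at 80% power | CI half-width (SD) |
|---|---|---|---|---|---|
| 18 | 2.970 | 2.110 | 0.80 | 0.70 | 0.50 |
| 14 | 2.619 | 2.160 | 0.68 | 0.81 | 0.58 |
| 12 | 2.425 | 2.201 | 0.60 | 0.89 | 0.64 |
| 9 | 2.100 | 2.306 | 0.46 | 1.07 | 0.77 |
| 6 | 1.715 | 2.571 | 0.29 | 1.43 | 1.05 |

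**4. Whether a pooled test reflects the burn effect**

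Simulation for a single endpoint, 18 evaluable, change SD of 1 in both groups, 100,000 runs per case. The splits and effects are assumptions. Entries are the proportion of pooled tests that are significant.

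| Burn effect / non-burn effect | 14 burn, 4 non-burn | 9 burn, 9 non-burn |
|---|---|---|
| 0.7 / 0 | 55% | 25% |
| 0 / 0.7 | 8% | 25% |
| 0 / 1.4 | 15% | 65% |

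The 25% can be checked by hand. At 9/9 with effects 0.7 and 0, the pooled mean is 0.35 and the pooled SD is √(1 + 0.35²) = 1.06, so the standardised effect is about 0.33, under half of the planned 0.7. The two 9/9 cases with a single effect of 0.7 are mirror images, so the pooled p-value cannot tell them apart.

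**The case against.** **The wider population is described consistently except in Section 1.** Sections 4 and 6 agree with each other. The aims in Section 3 and the primary outcome in Section 4 are not restricted to burns, so the enrolled group does address Aim 1. This stands, and it means that most of the conflict can be removed by rewording Section 1. It does not supply a result for burns.

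**The chronic phase is required of everyone.** Reading only inclusion 3 and exclusion 4, one might infer that non-burn patients enter with no chronic-phase condition. The documents do not support that, because Section 4 and the opening of Section 6 both impose it. What remains is that the numbered criteria do not repeat it and the term has no meaning set out for non-burn causes. Stating that meaning would not by itself stop a chronic disease from progressing over 8 weeks.

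**Concurrent change is partly controlled.** Sections 6 and 7 suspend other treatments and exclude surgery, other stretching and new topical products. That limits outside influences, but not the course of the underlying condition.

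**The analysis is not one pooled test.** Section 14 works expression by expression, and nine are listed. A breakdown by cause is therefore several rows of estimates in small groups. This stands and is counted as a cost below.

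**This is a pilot.** Section 14 plans individual trend plots, Section 4 speaks of change within a single subject, and a larger trial is to follow. These soften the point. But the plan also specifies power and significance tests, and Section 1 attaches a decision to the results.

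**The risk depends on the mix.** With 4 non-burn patients of 18, a false impression of burn efficacy arises in 8% to 15% of the simulated cases. It becomes large only when non-burn patients are a large share. This stands.

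**Conclusion.** The target population is internally contradictory. Section 1 confines the efficacy question to chronic facial burns, Sections 4 and 6 enrol other causes, and Section 14 provides nothing by cause. As written, the plan would allow a mixed-cause result to be presented as efficacy in burns. The chronic-phase requirement covers all participants but is carried unevenly into the numbered criteria and is defined for burns only.

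The size depends on a burn share that the documents do not give. Over the assumed range of 14 down to 6 evaluable burn patients, power at 0.7 for burns alone falls from 0.68 to 0.29, against 0.80 for the whole group. In the simulated cases with no burn effect, a pooled test is significant 8% or 15% of the time at 14/4, and 25% or 65% at 9/9, for non-burn effects of 0.7 or 1.4. These figures assume equal SDs and a single endpoint.

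Two stronger inferences are not supported. The sample size of 20 is not wrong: it reproduces. Nor can it be said that the pooled analysis fails to address the burn hypothesis. If nearly all enrolled patients have burns, it largely does. The point is that the plan neither secures nor reports that mix.

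**What to change.** 1. **Sections 1 and 6.** Make the population statement and hypothesis in Section 1 match the population that Section 6 enrols.
2. **Sections 4, 6 and 7.** Reconcile inclusion 3 and exclusion 4 with the all-participant chronic-phase requirement in Section 4 and the opening of Section 6. State what that requirement means for non-burn causes. The content of that definition is for the investigators.
3. **Section 14, reporting.** Report the number of burn and non-burn participants. For each primary per-expression change already analysed, give the mean, SD and 95% confidence interval for burn and non-burn participants beside the pooled estimate. No subgroup tests are needed.
4. **Section 14, interpretation.** State that power of 0.80 at effect size 0.7, with about 18 evaluable, is for the mixed group, and that any statement about burns rests on the burn estimate.

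**Cost.** Changes of wording, and additional descriptive rows for each expression. No patients, visits or measurements are added. The burn intervals will be wide: with 9 burn patients, about ±0.77 SD against ±0.50 SD for the pooled group of 18.
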